1.0 INTRODUCTION

The purpose of this document is to detail the planned statistical analysis and data presentations that will be performed to support the Clinical Study Report (CSR) for Gage, LLC study protocol GDC-229-002. The analyses detailed herein are based on the study protocol (Version 01.00, dated 23JAN2017) and electronic case report forms (eCRFs, dated 16FEB2017). Any post-hoc or unplanned analyses not identified in this SAP will be clearly identified in the CSR.

2.0 PROTOCOL SUMMARY

2.1 Background

Bacterial vaginosis (BV) is a common bacterial infection in women. BV is typically diagnosed using Amsel's criteria (Amsel 1983). The four Amsel's criteria used to determine a clinical diagnosis of BV are as follows: (1) vaginal pH > 4.5; (2) positive "whiff" test ("fishy" odor); (3) homogenous, non-viscous, off-white (milky or gray) discharge; (4) the presence of $\geq 20\%$ clue cells.

Oral and topical antibiotics are used to treat BV. Metronidazole was approved for use in the United States in 1963 and is currently a first-line treatment for BV ([Flagyl \(metronidazole\) NDA 012623, Approval Date 18JUL1963](#)). Gage Development Company is developing a drug product candidate that is designed to be therapeutically equivalent to the marketed drug metronidazole 0.75% vaginal gel for the treatment of BV.

2.2 Objectives

The primary objective of this study is to assess the therapeutic equivalence of an experimental formulation of a metronidazole 0.75% vaginal gel (GDC-229; test product) versus metronidazole 0.75% vaginal gel (Oceanside Pharmaceuticals) in subjects with BV. A vehicle (placebo) arm is included for assay sensitivity purpose.

The secondary objective of this study is to evaluate the safety and tolerability of GDC-229 versus metronidazole 0.75% vaginal gel (Oceanside Pharmaceuticals) and vehicle (placebo) vaginal gel in subjects with BV.

2.3 Trial Design

This is a multicenter (with approximately 40 study sites), randomized, double-blind (for both subjects and investigators), vehicle-controlled bioequivalence study with a clinical endpoint. Following completion of the screening procedures, eligible subjects will be randomized in a blinded manner and in a 1:1:1 ratio to one of three treatment arms:

- GDC-229, the test product
- Reference product (metronidazole 0.75% vaginal gel by Oceanside Pharmaceuticals)
- Vehicle (placebo) vaginal gel.

There are three planned study visits as follows:

1. Study entry Visit (Day 1, screening and randomization);

2. Post-Treatment Assessment (Study days 8-15, i.e., 7 to 14 days after randomization), and
3. Test of Cure (Study days 22-31, i.e., 21 to 30 days after randomization).

Though early termination can occur anytime after enrollment, the study generally is up to 31 days in duration for each subject. The study treatment is to be administered intravaginally once daily at bedtime during Study Days 1 to 5.

All procedures and assessments associated with each study visit are shown in the [Appendix 5.1](#) of this SAP. Including a recruitment period of about seven months, the study duration is expected to be approximately eight months.

2.4 Study Endpoints

2.4.1 Primary Endpoint

The primary study endpoint is “Clinical Cure”, defined as the resolution at the Test of Cure visit of the following three abnormal BV signs included in Amsel’s criteria:

- Return to normal physiological vaginal discharge as determined by the investigator
- Negative whiff test
- The presence of clue cells at <20% of the total epithelial cells on microscopic examination of the saline wet mount.

2.4.2 Secondary Endpoints

The secondary efficacy endpoints are the “Bacteriological Cure” and the “Therapeutic Cure” at the Test of Cure visit (Visit 3). Bacteriological Cure is defined as Nugent’s score < 4 (via Gram stain central laboratory analysis). A Nugent’s score ≥ 4 is considered abnormal and represents an imbalance in vaginal flora that permits BV to manifest (Nugent 1991). Subjects who are responders are expected to achieve a normal Nugent’s score (i.e., 0 to 3) following the study treatment.

Therapeutic Cure is defined as having achieved Clinical Cure, vaginal pH of < 4.7, and Bacteriological Cure (Nugent’s score < 4) at Visit 3.

2.5 Sample Size Consideration

Assuming the test and reference products’ Clinical Cure rates are within 4% of each other, the placebo clinical cure rate is 20%, the test and reference clinical cure rates are at least 36.0% and 12.4% of randomized subjects do not qualify for the modified Intent-to-Treat (mITT) population (defined in [Section 3.4](#) of this SAP), then 603 subjects will be required to achieve at least 90% power for superiority and therapeutic equivalence (Schwebke 2015; Chavoustie 2015). However, the previous studies that were used to estimate effect size had significant differences in study design and definition of primary endpoint. Taking these differences into consideration, approximately 738 subjects were planned to be randomized. The assumption of a 36% test and reference clinical cure rate was derived after review of the FDA’s Statistical Review of Metronidazole vaginal gel 1.3% (Center for Drug Evaluation and Research 2014).

3.0 STATISTICAL METHODS

3.1 Statistical Handling Policy

3.1.1 Interim Safety Review

No formal interim analysis will be conducted. A blinded Medical Monitor will periodically perform a blinded review of adverse event data.

3.1.2 Analysis Conventions

This section details general approaches to be used for the statistical analyses. Departures from these general approaches may be outlined in the specific detailed sections of this statistical analysis plan, and will take precedence over the general approaches. The following approaches will be applied to all data presentations and analyses.

- Data listings will be provided for all CRF data with one listing for one CRF panel. All data listings will be sorted for presentation in the order of site identifier (ID), subject ID, and date of procedure or event.
- Statistical summary tables will be provided for most CRF data, and generated for each of the 3 treatment groups, and for overall subjects (i.e., 3 groups combined) when appropriate.
- Summary statistics will consist of the number and percentage of responses in each category for discrete (categorical) variables, and the number of non-missing observations (n), mean, median, standard deviation (SD), minimum, and maximum (abbreviated as “6-number statistics”) for continuous variables.
- All mean values will be formatted to one more decimal places than the measured value, and standard deviation values will be formatted to two more decimal places than the measured value. For median values, the same decimal place as the measured values will be reported, if that is feasible without losing accuracy; otherwise, median values will be formatted to one more decimal place than the measured values.
- All percentages will be rounded to one decimal place. The number and percentage of categorical responses will be presented in the form XX (XX.X), where the percentage is in the parentheses. The denominator for percentage calculations will be the number of non-missing observations (n) when this number is shown, or will be the total sample size of the relevant treatment group for tables like adverse events, medical histories, or other tables where this number of non-missing observations (n) is not presented.
- All statistical tests will use a significance level of $\alpha = 0.05$. Two-tailed tests will be performed for all analyses that use statistical testing.
- All p-values will be rounded to 3 decimal places. All p-values that round to 0.000 will be presented as ‘<0.001’, and p-values that round to 1.000 will be presented as ‘>0.999’. Any p-value ≤ 0.05 will be considered statistically significant and will be marked with one asterisk (e.g., 0.025*).

- All analysis and summary tables will have the population sample size in the column heading.
- Baseline is defined as the last data point on or before the day of randomization.
- Calculating change from baseline to a visit will be done as follows: Change from Baseline = Observed value at the visit – Baseline value.
- Subjects who have only baseline (without any post-baseline measurements) for a parameter at a visit, or only have post-baseline value for a parameter at a visit, will be excluded from the summary of change from baseline by visit for that parameter.
- Version 9.4 of SAS® or higher will be the statistical software package used to produce all statistical analysis tables and data listings.

3.2 Subject Disposition

Subject disposition will be summarized as follows: for the All Screened population with the following data:

- Number of informed consented subjects in each of the following 4 groups:
 - Screen failures
 - Placebo
 - GDC-229
 - Metronidazole
- Summary of screen failures by the reason for ineligibility for screen failed subjects
- The number and percentage of randomized subjects who completed or discontinued prematurely from the study, the number and percentage of subjects who discontinued by each reason for all subjects.
- A listing of randomized subjects who discontinued prematurely from the study. The listing will include information about study site ID number, subject ID number, age, number of doses used, and reason for discontinuation.
- The number and percentage of randomized subjects at each study visit.
- The number of randomized subjects who were enrolled, completed or discontinued prematurely at each study site.

The Disposition page of the CRF will be used to determine those subjects that discontinued prematurely from the study.

3.3 Protocol Deviations

Protocol deviations will be summarized by type of deviations listed on the CRF. Both the number of deviation events and distinct number and percentage of subjects will be presented for each type of deviation by treatment group and for all Intent-to-Treat subjects.

3.4 Analysis Populations

All Screened Population: all subjects who signed Consent Form and screened at the study sites.

Intent-to-Treat (ITT) Population: All randomized subjects.

Safety Population: All randomized subjects who received at least 1 dose of study drug. If the drug accountability is unknown (e.g., due to being lost to follow-up after being randomized) then subjects will be assumed to have taken study drug and included in the safety population. Subjects reporting 0 doses will be excluded.

Modified Intent-to-Treat (mITT) Population: a subset of the Safety Population who also met all 4 Amsel's criteria at baseline, but excluding those who subsequently demonstrate a positive or indeterminate test result for other concomitant vaginal or cervical infections at baseline (e.g. *C. trachomatis*, *N. gonorrhoeae*) which may interfere with the efficacy assessment for BV, or who have a baseline Nugent's score < 4. If baseline STI value is missing, use the Post-Treatment Assessment Visit infection test result. Subjects without a Nugent's score at baseline will be excluded from the mITT population.

Per Protocol (PP) Population: All mITT subjects except for those who had at least one of the protocol deviations listed below. If lack of efficacy (LOE) is the discontinuation reason and the subject took at least 3 doses, then the subject will be included in PP as a treatment failure and then the 6 protocol deviations below will not exclude those subjects:

1. Used topical or systemic antimicrobial drugs after randomization, this includes the following drug classes: antimycotics, antibacterials, antiprotozoals, gynecological anti-infectives, antiseptics and antifungals.
2. Used non-study vaginal products during the study
3. Did not start treatment within 2 days of randomization
4. Took less than 5 doses of study drug
5. Test of cure visit (V3) was not in the Study Day 22 – 31 window, i.e., Visit 3 was not 21 – 30 days after randomization
6. Test of cure visit (V3) not done

Other important violations that represent material non-compliance with study drug or protocol that would impact the primary and secondary efficacy endpoints will be reviewed prior to database lock (i.e., before unblinding). These will be documented in the Evaluability Memo which will be included in the clinical study report.

Subjects in the mITT population who discontinue early from the study, and do not have an assessment of Clinical Cure or Bacteriological Cure will be included in the mITT population as treatment failures. These subjects without actual outcomes, but are classified as treatment failures will not be included in the PP analysis population.

sm **W W I** **W**

Subject demographics and pre-treatment characteristics will be summarized for the ITT analysis population, and some of these summaries may also be done for other populations when deemed important.

sharp

A summary of demographics and subject characteristics will be created for the ITT, Safety, mITT, and PP populations, and include age, race, ethnicity, height, weight, and body mass index (BMI) at the study entry visit with:

- 6-number statistics (number of non-missing observations, mean, median, SD, minimum, and maximum) for age, height, baseline weight, baseline BMI (to be calculated, see formula in [Section 3.8.4](#)) by treatment group and for all subjects.
- Age will be calculated (with the INTCK function in SAS®) using the study entry visit date and the date of birth. Subject age (years) will also be categorized as 18-20, 21-30, 31-40, 41-50, 51+, and then summarized categorically along with race, ethnicity.
- BMI at the study entry visit will also be categorized as: Underweight (< 18.5), Normal (18.5 – 24.9), Overweight (25.0 – 29.9), and Obese (≥ 30.0). The number and percentage of subjects in each of these categories will be presented by treatment group and for all subjects.

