3.5.3.3.1 General

Patients with severe hepatic disease metabolize metronidazole slowly. This results in the accumulation of metronidazole and its metabolites in the plasma. Accordingly, for such patients, metronidazole vaginal gel should be administered cautiously.

Known or previously unrecognized vaginal candidiasis may present more prominent symptoms during therapy with metronidazole vaginal gel. Approximately 6-10% of patients treated with metronidazole vaginal gel developed symptomatic Candida vaginitis during or immediately after therapy.

Disulfiram-like reaction to alcohol has been reported with oral metronidazole, thus the possibility of such a reaction occurring while on metronidazole vaginal gel therapy cannot be excluded.

Metronidazole vaginal gel contains ingredients that may cause burning and irritation of the eye. In the event of accidental contact with the eye, rinse the eye with copious amounts of cool tap water.

3.5.3.3.1.1 Information for the Patient:

The patient should be cautioned about drinking alcohol while being treated with metronidazole vaginal gel. While blood levels are significantly lower with Metronidazole Vaginal Gel than with usual doses of oral metronidazole, a possible interaction with alcohol cannot be excluded.

The patient should be instructed not to engage in vaginal intercourse during treatment with this product (in addition, the protocol requires that the subject not engage in vaginal intercourse for the two days following treatment or for 48 hours prior to Visits 2 and 3).

3.5.3.3.1.2 Drug Interactions

Oral metronidazole has been reported to potentiate the anticoagulant effect of warfarin and other coumarin anticoagulants, resulting in a prolongation of prothrombin time. This possible drug interaction should be considered when metronidazole vaginal gel is prescribed for patients on this type of anticoagulant therapy.

In patients stabilized on relatively high doses of lithium, short-term oral metronidazole therapy has been associated with elevation of serum lithium levels and, in a few cases, signs of lithium toxicity.

Use of cimetidine with oral metronidazole may prolong the half-life and decrease plasma clearance of metronidazole.

3.5.3.3.1.3 Drug/Laboratory Test Interactions

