4.8.3 Screening for Sexually Transmitted Infections

At the Entry Visit (Visit 1) pelvic examination, a sample will be collected for assessment of sexually transmitted infections (STI) for *Chlamydia trachomatis*, *Neisseria gonorrhoeae*.

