4.8.4 Microbiological Sample

A wet smear microbiological sample will be collected at each visit in order to determine if Amsel's criteria are met/or resolved. Evidence of any vulvovaginitis other than BV. (e.g., vulvovaginal candidiasis, *Trichomonas vaginalis*, *Chlamydia trachomatis*, *Neisseria gonorrhoeae*, active Herpes simplex, or active HPV will also be ruled out in order to ensure study eligibility. In addition, a specimen for Gram stain will be collected at Visits 1 and 3. Details for collection, preparation, and evaluation of microbiological samples by the central lab will be provided in the study laboratory manual.

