5.1 Entry Visit (Visit 1)

During the screening portion of the Entry Visit (Visit 1), the following should be completed:

- Obtain written informed consent.
- Perform urine pregnancy test.
- Review and confirm inclusion and exclusion criteria.
- Obtain demographic data.
- Collect medical and gynecological history, including sexual history, information on the subject's menstrual cycle, and history of STIs.
- Obtain vital signs after sitting for 5 – 10 minutes ([Section 4.5](#)).
- Record height and weight.
- Record current medications and prior medications taken within three months prior to the start of screening, in addition to the indication for the medication and reasons for discontinuing medication.
- Perform complete physical and pelvic examination including a vaginal wall inspection (i.e., a naked eye inspection) as well as an examination of the cervix.
- Perform urine drug screening.
- Collect Chlamydia and gonorrhea swab samples for central laboratory analysis.
- Collect a swab sample for central laboratory Nugent's analysis for BV via Gram stain.
- Screen for presence of BV by assessing the subject for presence of the four Amsel's criteria. (Note: The four Amsel's criteria are the only BV diagnostic criteria on which the decision to randomize is made; Nugent's result is not used for randomization decisions). If the results of the Amsel's screening tests are positive and the subject is eligible according to all other inclusion/exclusion criteria, the subject can be randomized to treatment:
 - Clinical diagnosis of BV (e.g., thin, homogeneous off-white [milky or grayish] vaginal discharge associated with minimal or absent pruritus inflammation); AND
 - Saline wet mount of vaginal discharge demonstrating the proportion of clue cells to be $\geq 20\%$ of the total epithelial cells; AND
 - Vaginal secretion pH > 4.5 ; AND

- Positive “whiff test” after addition of a drop of 10% KOH to vaginal discharge.
- Assess the saline wet mount for evidence of any vulvovaginitis other than BV. (e.g., vulvovaginal candidiasis, *Trichomonas vaginalis*, *Chlamydia trachomatis*, *Neisseria gonorrhoeae*, active herpes simplex, or active HPV) per laboratory manual.
- An overall determination of the subject’s eligibility will be made based on the results of the assessments noted above as well as all inclusion and exclusion criteria (see [Section 3.3](#)).

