5.6 Schedule of Assessments

The schedule of assessments is provided in [Table 3](#).

Table 3 Schedule of Assessments

Visit	Visit 1	Visit 2	Visit 3	
Visit Name	Entry Visit	Post-Treatment Assessment	Test of Cure	Early Termination ^a
Study Day(s)	1	7 to 14 days	21 to 30	
Informed consent	X			
Inclusion/exclusion criteria	X			
Demographics	X			
Medical and gynecological history	X			
Physical examination	X		X	X
Pelvic examination	X	X	X	X
Height	X			
Weight	X		X	X
Vital signs (after sitting for 5 - 10 mins)	X	X	X	X
Concomitant medications	X	X	X	X
Randomization ^b	X			
Dispense study medication ^c and dosing instructions	X			
Collect study medication		X		X ^d
Assessment of local site reactions		X	X	X
Adverse events	X	X	X	X
Urine pregnancy test	X	X	X	X
Urine drug screen	X			
Amsel's criteria evaluations:				
-Assessment of vaginal discharge	X	X	X	X
-KOH Whiff Test	X	X	X	X
-Saline Wet Mount	X	X	X	X
-pH	X	X	X	X
Collection of samples for Nugent's score based on Gram stain (send to central laboratory)	X		X	X
Collection of samples for STI assessment ^e (send to central laboratory)				
	X			

- a. At any time a subject decides to discontinue her participation in the study or is discontinued from the study for any other reason, she will be advised to complete the Early Termination procedures.
- b. Randomization to occur if the results of the full set of Amsel's criteria are positive.
- c. Study medication will be dispensed at Visit 1. The subject will be instructed to self-administer study medication intravaginally once daily at bedtime for 5 consecutive days.
- d. Unless collected at previous visit.
- e. Central laboratory analysis for *Chlamydia trachomatis* and *Neisseria gonorrhoeae*.

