3.7.3 Other Outcome Measurements

The other assessments as follows (each with “Yes”, or “No” answer) on “Study Procedure” form will be presented in data listing:

- Was there a vaginal secretion with pH greater than 4.5?
- Was the saline wet mount assessed for evidence of any other vulvovaginitis other than BV?

- Did the wet mount contain any evidence for candidiasis, Trichomonas vaginalis, Chlamydia trachomatis, Neisseria gonorrhoeae, active herpes simplex, or active HPV?
- Was the urine drug screen performed?
- Were any of the results positive?
- In the last 48 hours have you used any spermicides, tampons, douches, diaphragms, condoms or other intravaginal product?
- Since your last visit have you used any spermicides, tampons, douches, diaphragms, condoms or other intravaginal product?
- Have you had intercourse within the 48 hours prior to a visit?

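### Does the fallback from a missing baseline STI result to a Visit 2 infection test (and the Visit 3 day label) make the mITT and PP populations unreliable?

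*SAP*

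**What the plan says.** SAP 3.4 builds the mITT population from the Safety population. Among other conditions, it removes women with a "positive or indeterminate test result for other concomitant vaginal or cervical infections at baseline". Two missing-data rules follow. For infections: "If baseline STI value is missing, use the Post-Treatment Assessment Visit infection test result". For the Nugent score, a woman with no baseline value is excluded. No rule is given for a woman with no STI result at either visit. The mITT definition in Protocol 9.2 has no fallback.

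Protocol 4.8.3 fixes the timing of the STI sample: "At the Entry Visit (Visit 1) pelvic examination, a sample will be collected for assessment of sexually transmitted infections". In Protocol Table 3 and in SAP 5.1, the row "Collection of samples for STI assessment" is marked under Visit 1 only, and a footnote limits it to central-laboratory analysis for *C. trachomatis* and *N. gonorrhoeae*.

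The wet mount is a separate procedure. At entry the site must "Assess the saline wet mount for evidence of any vulvovaginitis other than BV", and Protocol 4.8.4 says these other infections "will also be ruled out in order to ensure study eligibility". At Visit 2, Protocol 5.2 uses the wet mount for clue cells. SAP 3.7.3 plans a data listing of a form item that asks: "Did the wet mount contain any evidence for candidiasis, Trichomonas vaginalis, Chlamydia trachomatis, Neisseria gonorrhoeae, active herpes simplex, or active HPV".

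On timing, the text of Protocol 3.1 and 5.3 puts Visit 3 at 21 to 30 days from randomization or Visit 1. Tables 1 and 3 label it Day 21 to 30, with Visit 1 as Day 1. SAP 2.3 and PP deviation 5 in SAP 3.4 use Study Day 22 to 31 and state in the same place that this means 21 to 30 days from randomization.

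**The concern.** The mITT population carries both superiority tests against placebo, and the PP population used for equivalence is nested in it. Membership should depend on baseline facts alone. A result obtained 7 to 14 days after randomization can reflect treatment. The SAP also moves from an STI value to a broader infection test without naming one.

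Only the wet smear is scheduled as microbiology at Visit 2, so a programmer might turn to the wet-mount item, which includes candidiasis. Protocol 3.5.3.3.1 reports: "Approximately 6-10% of patients treated with metronidazole vaginal gel developed symptomatic Candida vaginitis during or immediately after therapy". On that reading, exclusions could differ between active and placebo arms, and two programmers could build different mITT sets.

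The day labels raise a smaller worry. A site that booked by Table 1 or Table 3 could see a woman on Study Day 21, and PP deviation 5 would then remove her.

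**Working it through.** **1. What the fallback can do when followed as written.**

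- *No Visit 2 STI test was done* (the scheduled case). The criterion excludes only on a positive or indeterminate result. There is none, so she is not excluded. The contrast with the Nugent rule, where absence is expressly made an exclusion, supports this.
- *An unscheduled chlamydia or gonorrhea test was done at Visit 2.* It replaces the missing value. Inclusion criterion 3 asks women to refrain from vaginal intercourse on Days 1 to 7 and for 48 hours before Visit 2, so a positive result there plausibly reflects infection already present at entry.
- *The Visit 2 wet mount is used.* The rule starts from a missing STI value, and the protocol limits the STI sample to two organisms. Candida is not one of them. The protocol asks for the wet-mount rule-out at entry, for eligibility, and SAP 3.7.3 only lists the item, with no link to SAP 3.4.

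**2. Size under the unsupported wet-mount reading.** The documents give no rate of missing STI results, so *m* is assumed. Inputs are 246 women per arm (Protocol 3.1), a 36% active cure rate (Protocol 9.1) and a Candida share *c* of 0.06 to 0.10 (Protocol 3.5.3.3.1).

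- Missing per arm = 246 × *m*
- Excluded per active arm = 246 × *m* × *c*
- Largest rise in cure rate, if every excluded woman were a failure = 0.36 / (1 − 0.10 *m*) − 0.36

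| Assumed *m* | Missing per arm | Excluded per active arm | Largest rise (percentage points) |
|---|---|---|---|
| 1% | 2.5 | 0.15 to 0.25 | 0.04 |
| 2% | 4.9 | 0.30 to 0.49 | 0.07 |
| 5% | 12.3 | 0.74 to 1.23 | 0.18 |

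The planned active-minus-placebo difference is 36 − 20 = 16 points. Both active arms contain metronidazole 0.75%, so similar Candida rates would largely cancel in the test-minus-reference difference.

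**3. The plan's own sample size, to see how much room there is.** A two-sided 5% comparison of 36% with 20% at 90% power, with continuity correction, needs 176 per arm. 176 / (1 − 0.124) = 200.9, rounded up to 201, and 3 × 201 = 603, as stated. At 95% power the same formula needs 215 per arm. 215 / 0.876 = 245.4, rounded up to 246, and 3 × 246 = 738, the number to be randomized. Starting from 215 per arm, an assumed 10% loss from every arm lowers superiority power (36% against 20%, no continuity correction) from 96.1% to 94.2%.

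**4. The Visit 3 window.** With Visit 1 as Day 1, study day = days from randomization + 1. The SAP's Study Day 22 to 31 is therefore 21 to 30 days from randomization, the same as the protocol's text. Read literally on a Day 1 scale, the table label is 20 to 29 days. The two differ only at Study Day 21 (in the label, not in the SAP window) and Study Day 31 (the reverse). The duration entry in the protocol synopsis ties Days 21 and 30 to time after randomization, so the label is best taken as loosely written.

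PP losses through the window touch only the equivalence test. Its power, by exact binomial calculation with the SAP 3.7.1 limits, test 36% and reference 40%, is 95.4% at 215 per arm. It is 93.6% at 194 (an assumed 10% loss to other deviations) and 90.6% at 174 (about a further 10% lost to Study Day 21 visits).

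**The case for a change.** The strongest case for acting is that a rule feeding the superiority population should leave nothing to interpretation. SAP 3.4 does not name the test or say what applies when both results are absent, and one or two sentences before unblinding would close the gap. That description of the text is right.

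Two things weaken it as a reason for change. The proposed remedy is to let only Visit 1 results exclude and to keep women with no result. Where no Visit 2 STI test exists, that already follows from the rule. Where one does exist, the remedy would discard information about a probable baseline infection, so it trades one small imperfection for another. A Visit 2 result is not strictly a baseline value, and infection acquired between visits cannot be ruled out, but neither route is clearly better. Also, the eCRF and the laboratory manual, which may identify the test, are not among the documents reviewed.

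On the window, joint power for all three tests can be brought below 90%: with test 36% and reference 40%, it is 89.9%, 89.1% and 87.8% at 190, 184 and 174 PP subjects per arm. That requires an assumed 10% loss to other deviations, a further assumed 2% to 10% of visits on Study Day 21 and the full 4-point difference. With both active arms at 36%, joint power is still 90.7% at 174. These figures describe general PP attrition, not a defect in the window.

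**Conclusion.** No change is called for. The missing name of the Visit 2 test is a gap that an analyst would fill by looking for a chlamydia or gonorrhea result and, finding none, leaving the woman in. The planned listings of STI tests (16.2.8.2) and of subjects excluded from efficacy (16.2.3) make each use of the rule visible. Even the reading that the documents do not support moves an active cure rate by at most 0.18 percentage points, assuming 5% of baseline results missing, 10% Candida and every excluded woman a failure.

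The Visit 3 label is a clerical one-day mismatch inside the protocol. The SAP's PP rule is unambiguous and agrees with the protocol's text. The missing-STI rate and the visit-day distribution are unknown, so these sizes are illustrations. Nothing in the documents suggests that either point would alter the superiority or equivalence conclusion.
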